8.6. Safety and Tolerability Assessments

8.6.1. Adverse Events

All AEs will be coded using the Medical Dictionary for Regulatory Activities (MedDRA) Version 23.0. All AEs will be assigned severity grade using Common Terminology Criteria for Adverse Events (CTCAE) Version 5.0.

A treatment-emergent adverse event (TEAE) will be defined as an AE that starts during or after LOXO-305 dosing, or starts prior to dosing and increases in severity after LOXO-305 dosing.

A treatment-related TEAE will be defined as a TEAE with a relationship of related to the study treatment, as determined by the investigator.

All AEs will be listed. In addition to the data recorded in the database, the listings will include derived onset time and duration. Onset time will be calculated from the time of dosing for TEAEs only.

The frequency of subjects with TEAEs and the number of TEAEs will be summarized for the following categories:

- TEAEs (overall, serious, leading to discontinuation, and leading to death) by treatment
- TEAEs by severity and treatment
- Treatment-related TEAEs (overall, serious, leading to discontinuation, and leading to death) by treatment
- Treatment-related TEAEs by severity and treatment

The frequency of subjects will be summarized separately for TEAEs and treatment-related TEAEs by the following:

- System organ class, preferred term, and treatment
- Preferred term and treatment
- System organ class, preferred term, day of onset, and treatment

For the AE data the following rules will apply:

- For the derivation of TEAE status: If the start date/time of an AE is incomplete or missing, an AE will be assumed to be a TEAE, unless the incomplete start date/time or the end date/time indicates an AE started prior to dosing.
- For the derivation of treatment-related TEAE status: If the study treatment relationship for a TEAE is missing, a TEAE will be assumed to be a treatment-related TEAE.
- For the derivation of onset time: If the start date/time of an AE is missing, onset time will not be calculated. If the start date/time of an AE is incomplete, where possible, the minimum possible onset time will be calculated and presented in ‘ \geq DD:HH:MM’ format (eg, if the date/time of dosing is 01MAY2019/08:00 and recorded start date/time of an AE is 03MAY2019, then the minimum possible onset time will be calculated by assuming the AE started at the first hour and minute of 03MAY2019 [03MAY2019/00:00], thus will be presented as onset time \geq 01:16:00 in the listing).
- For the derivation of duration: If the end date/time of an AE is missing, duration will not be calculated. If the start or end date/time of an AE is incomplete, where possible, the maximum possible duration will be calculated and presented in ‘ \leq DD:HH:MM’ format (eg, if the start of an AE date/time is 01MAY2019/08:00 and its recorded end date/time is 03MAY2019, then the maximum possible duration will be calculated by assuming the AE ended at the last hour and minute of 03MAY2019 [03MAY2019/23:59], thus will be presented as duration \leq 02:15:59 in the listing).
- For the calculation of summary statistics: If the severity of a TEAE is missing, a TEAE will be counted under the maximum severity possible, up to Grade 4 in the absence of a fatal outcome.

- For the calculation of summary statistics: If a subject experienced multiple TEAEs with the same preferred term for the same treatment, this will be counted as 1 TEAE for that treatment under the maximum severity recorded.

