Unless a subject withdraws consent or is withdrawn from the study and does not complete the follow-up phone call, all subjects must be followed until EOS. Subjects with AEs that are assessed as related to study drug by the Investigator (or designee) which are ongoing at EOS may continue to be followed until the symptoms or value(s) return to normal, or acceptable levels, as judged by the Investigator (or designee) and confirmed by the Sponsor. The Investigator (or designee) should use appropriate judgment in ordering additional tests as necessary to monitor the resolution of events. The Sponsor may request that additional safety tests be performed.

Subjects will receive a follow-up phone call 7 days (\pm 2 days) after EOT or ET to determine if any SAE or drug-related AE has occurred since the EOT or ET visit.

At all times, a subject may be required to remain at the CRU for longer at the discretion of the Investigator (or designee).

Any event that meets the criteria of a suspected unexpected serious adverse reaction (SUSAR) will be reported to the Institutional Review Board (IRB) according to CRU policy by the Investigator (or designee) and to regulatory authorities by the Sponsor (or Sponsor designee) according to regulatory authority requirements. Refer to Reference Safety Information in the current IB¹ for LOXO-305 for expected adverse reactions.

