AEs and serious AEs (SAEs) will be collected beginning at informed consent. AEs will be reported throughout the study (ie, from signing of the ICF until End of Study [EOS], or until ET if the subject discontinues from the study and does not complete a follow-up phone call), either as subject medical history (if the event is reported as beginning prior to signing of the ICF or if the event occurs prior to study drug administration on Day 1 and is assessed as not related to study procedures by the Investigator [or designee]) or as AEs (if the event occurs after signing of the ICF but prior to study drug administration on Day 1 and is assessed as related to study procedures by the Investigator [or designee], or if the event occurs after study drug administration on Day 1 through EOT or ET regardless of relationship to study drug). From EOT or ET through EOS, only AEs assessed as related to study drug by the Investigator (or designee) are to be reported. All SAEs that develop from the time of ICF signing until EOS (or ET, if the subject discontinues from the study and does not complete a follow-up phone call) are to be reported.

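### The all-cause TEAE tables pool a period with full AE recording and a follow-up period in which non-serious events are recorded only if judged drug-related

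*SAP*

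**What the plan says.** The collection rule is the same in the protocol synopsis, Protocol 3.1 and 7.2.1, Appendix 4 (footnote j) and SAP 4. It has three parts:

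- After dosing, an event is an AE "or if the event occurs after study drug administration on Day 1 through EOT or ET regardless of relationship to study drug".
- After that, the entry condition changes: "From EOT or ET through EOS, only AEs assessed as related to study drug by the Investigator (or designee) are to be reported".
- Serious events are exempt: "All SAEs that develop from the time of ICF signing until EOS" are to be reported, with no causality condition.

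Protocol 7.2.1 gives the follow-up call a matching purpose, "to determine if any SAE or drug-related AE has occurred since the EOT or ET visit".

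SAP 8.6.1 defines treatment emergence by onset, or by worsening of an earlier event, relative to dosing: "A treatment-emergent adverse event (TEAE) will be defined as an AE that starts during or after LOXO-305 dosing". Neither it nor the definition in Protocol Appendix 1 gives an end date. The planned tables include "TEAEs (overall, serious, leading to discontinuation, and leading to death) by treatment", the same by severity, and SOC and preferred-term tables, one of them by day of onset. The related tables are a subset: "A treatment-related TEAE will be defined as a TEAE with a relationship of related to the study treatment, as determined by the investigator".

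**The concern.** Safety and tolerability is the primary objective. The study is open-label and has no control arm. In that setting the all-cause count is the main descriptive safeguard against a wrong causality call, because it does not depend on that call. After EOT/ET it does depend on it for non-serious events: causality decides whether the event exists in the database at all. A non-serious event wrongly judged unrelated in that period leaves no AE record for the sponsor to look at again.

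The tables carry no sign of this. A reader of the overall TEAE table would take it as all-cause through the end of the study. A reader of the day-of-onset table would see unrelated non-serious events stop after about Day 8, and could not tell that the recording rule caused it.

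The causality categories in Protocol Appendix 1 leave room for such calls. Not related requires a time course that rules out a causal link and another suspected cause. Related requires a compatible time course and no other identifiable cause. An event with a compatible time course and a possible alternative cause meets neither description.

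**Working it through.** **1. The rules side by side**

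- Dosing to EOT/ET: all AEs, any relationship.
- EOT/ET to EOS, non-serious: related only.
- EOT/ET to EOS, serious: all, any relationship.
- TEAE tables: onset or worsening from dosing, no end.

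The serious and fatal rows follow one rule throughout. The rows that include non-serious events cross a change of rule at EOT/ET. SAP 8.1 describes what listings contain and when a subject counts as having completed the study; it does not end the TEAE window.

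**2. Length of the filtered period**

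EOT is at 168 hours, which is 7 postdose days. The call is 7 days (±2) after EOT or ET. As a check on the windows, 28 days of screening + 9 of confinement + 9 of follow-up = 46, the stated duration; with the nominal 7 days of follow-up it is 44.

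For a subject who completes Day 8, with f days of follow-up, the filtered share of postdose time is f/(7 + f):

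- f = 5: 5/12 = 42%
- f = 7: 7/14 = 50%
- f = 9: 9/16 = 56%

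For an early terminator the all-cause period ends at ET, so its length varies between subjects.

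**3. Direction**

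Let R be all related TEAEs, U1 the unrelated TEAEs that are recorded, and U2 the unrelated non-serious follow-up events that are not.

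- All-cause count: tables show R + U1; complete collection gives R + U1 + U2. The shortfall is U2.
- Related count: R in both.
- Related share: tables imply R/(R + U1); complete collection gives R/(R + U1 + U2). The first is never below the second, and is strictly higher only when R > 0 and U2 > 0.

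A separate SAP rule can push the share the same way: "If the study treatment relationship for a TEAE is missing, a TEAE will be assumed to be a treatment-related TEAE".

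**4. Possible size (assumed rates)**

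Assume a constant rate of unrelated non-serious events, so U2 = U1 × f/7, and no unrelated follow-up SAEs. Scale events up to EOT to 1, with 40% related (0.4 related, U1 = 0.6), and f = 7, so U2 = 0.6.

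- No related follow-up event: tables 0.4/1.0 = 40%; complete 0.4/1.6 = 25%.
- Related follow-up events equal to 25% of those before EOT (R = 0.5): tables 0.5/1.1 = 45.5%; complete 0.5/1.7 = 29.4%; a table cut at EOT gives 40%.

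Over in-house related shares of 20% to 60% and f of 5 to 9, the excess over complete collection runs from about 7 to about 20 points:

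- Low end (20%, f = 5, no related follow-up event): 20.0% − 0.2/1.571 = 20.0% − 12.7% = 7.3 points.
- High end (60%, f = 9, no related follow-up event): 60.0% − 0.6/1.514 = 60.0% − 39.6% = 20.4 points.

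If U2 = 0 the excess is zero.

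**5. Chance that any event is lost**

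With 24 subjects and an assumed probability p that a subject has an unrelated non-serious event in follow-up, the chance of at least one is 1 − (1 − p)^24.

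- p = 2%: 38%, with 0.5 subjects expected.
- p = 20%: 99.5%, with 4.8 subjects expected.

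**The case against.** The collection rule is deliberate, stated in the same terms throughout, and applied alike to every cohort, so no distortion between doses is shown. Escalation uses safety data through 168 hours (Protocol 3.1 and 5.5), which for subjects completing Day 8 lies wholly within the period of full recording. The toxicity criteria count drug-related events only. By 168 hours some 7 to 8 half-lives have passed (168/24 = 7 from the statement that 72 hours is about 3 half-lives; 168/20 = 8.4 from the estimated 20 hours). Half of the calendar time is therefore not half of the expected drug effects. All AEs are listed with onset time, and the day-of-onset tables would let a careful reader isolate late events. The TFL shells, which may carry footnotes, are not among the documents. The healthy-volunteer experience described is sparse: in 10 subjects all TEAEs were judged related and came from 1 subject, and 3 further subjects had none.

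All of this stands, and it limits the point to the labelling and completeness of descriptive tables. It does not remove it. A listing can separate the late events that were recorded; it cannot show those that were not.

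Three stronger readings are tempting and are not supported:

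- That every follow-up event passes the causality filter. SAEs do not.
- That the tables do overstate the related share. No such share is planned, and one derived by a reader is too high only if an unrelated non-serious event occurs in follow-up. The documents give no rate from which to say that it will.
- That related counts are inflated or escalation compromised. The rule leaves related counts unchanged, and escalation rests on data through 168 hours.

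**Conclusion.** The point holds for non-serious events. Their all-cause tables combine full recording up to EOT/ET with causality-filtered recording after it, over 50% (42% to 56%) of postdose calendar time for a subject who completes Day 8. The certain defect is that these tables are not all-cause for the whole window they cover and do not say so. An under-count of all-cause events, and with it an overstated reader-derived related share, is possible but conditional on unrelated non-serious events in follow-up. The 7 to 20 point range and the 38% to 99.5% chance rest on assumed rates and show scale only. The safety analysis is descriptive, so this is a low-priority, low-cost improvement.

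**What to change.** In SAP 8.6.1:

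- Tabulate both all-cause and treatment-related non-serious TEAEs by onset through EOT/ET. Cutting only the all-cause tables would let a related count exceed the overall count.
- Show events with onset after EOT/ET in a separate table labelled as related or serious only.
- Keep the serious and fatal rows through EOS, where collection is complete. State the window on each row, since a follow-up SAE would then appear in a serious row without being in the non-serious tables.
- State how an event with an incomplete onset date is assigned to a period.

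The cost is SAP wording and one extra table. If even that is unwelcome, a footnote stating the change of rule at EOT/ET is the minimum.

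Where conduct still allows, amend the protocol so that every AE reported at the follow-up call is recorded, with causality as an attribute and not as an entry condition. The call, the HDYF inquiry and AE collection are already scheduled there (Protocol Appendix 4). This adds a few mostly unrelated AE records and requires a protocol amendment. SAP 10 already reports all four dose levels as confirmed, so it may come too late, in which case the SAP change alone should be made.

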8.4. Safety Analysis

All safety assessments, including AEs and SAEs, vital sign measurements, clinical laboratory evaluations, physical examination results, concomitant medications, and 12-lead ECGs, will be tabulated and summarized where possible, using descriptive methodology, as needed, by timepoint. Unless otherwise specified, baseline value is defined as the last non-missing measurement before administration of LOXO-305. No formal statistical analyses are planned for the safety data. All safety data will be listed by subject.

Concomitant medications will be coded using the WHO Drug Dictionary (WHO Drug Global B3, September 2019) and AEs will be coded using MedDRA Version 22.1 (or higher). The incidence of AEs will be presented by severity and by relationship to study drug as determined by the Investigator ([or designee], [Appendix 1](#) for AE reporting). All TEAEs will be summarized by system organ class and preferred term.

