4. STUDY DESIGN

This is an open-label, single-ascending dose study to evaluate the safety, tolerability, and PK of LOXO-305.

Up to 4 cohorts are planned for evaluation. In each cohort, 6 healthy adult subjects are planned for evaluation. Subjects will participate in only 1 cohort. In each cohort, subjects will receive a single oral dose of LOXO-305 on Day 1. Each cohort will include a sentinel group

of 2 subjects which will be dosed at least 48 hours before the remaining 4 subjects (following review of available safety data).

A single oral dose of LOXO-305 will be administered on Day 1 for each cohort as follows:

- Cohort 1 (Treatment A): 300 mg
- Cohort 2 (Treatment B): up to 600 mg
- Cohort 3 (Treatment C): up to 900 mg

One additional cohort (6 subjects) may be enrolled if it is deemed appropriate to repeat any dose level, or to add an interim dose level or levels (equal to or lower than 900 mg), as determined by the Sponsor in consultation with the Investigator (or designee), depending on the safety, tolerability, and PK results from the prior cohort(s). Dosing will not exceed 900 mg in any subject, nor will any subject be given a dose for which the C_{max} would exceed 26,000 ng/mL.

Dose escalation to a higher dose level (ie, next cohort) will not take place until the Investigator (or designee) and the Sponsor have reviewed all pertinent safety/tolerability data (ie, physical examinations, 12-lead ECGs, vital sign measurements, clinical laboratory evaluations, and AEs) through a minimum of 168 hours (Day 8) and have determined that adequate safety and tolerability from the previous lower dose cohort has been demonstrated to permit proceeding to the next cohort. PK data through at least 72 hours (approximately 3 half-lives) after dosing will be reviewed to guide the dose-escalation decision. Data from a minimum of 4 subjects will be reviewed in order to make a dose escalation decision. Each cohort will include a sentinel group of 2 subjects will be dosed at least 48 hours before the remaining 4 subjects (following review of all available safety data).

Each treatment (A, B, and C) will be administered orally in the morning following a fast of at least 10 hours prior to and 4 hours after dosing.

The PK sampling will be obtained for 168 hours after administration of each dose of LOXO-305.

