5. SAMPLE SIZE JUSTIFICATION

This study is planned to enroll up to 24 healthy adult male and female subjects (women of non-childbearing potential only). Six subjects will participate in each cohort.

Replacement subjects may be enrolled only if deemed necessary by the Sponsor.

Every attempt will be made to enroll at least 1 subject of each sex in each cohort.

No formal statistical assessment of sample size has been conducted. The sample size chosen for this study is common in single-ascending dose studies and is considered sufficient to achieve the objectives of the study.

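### The SAP's rule for repeated preferred terms also governs the number of TEAEs, so event counts will fall short, overall and by severity, if any subject has the same term more than once

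*SAP*

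**What the plan says.** SAP Section 8.6.1 sets up two kinds of adverse event table.

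- The overview and severity tables, for all TEAEs and for treatment-related TEAEs, carry two quantities: "The frequency of subjects with TEAEs and the number of TEAEs will be summarized for the following categories".
- The tables by system organ class and preferred term carry subject counts only: "The frequency of subjects will be summarized separately for TEAEs and treatment-related TEAEs by the following".

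The last data-handling rule in the section begins "For the calculation of summary statistics: If a subject experienced multiple TEAEs with the same preferred term for the same treatment" and ends "this will be counted as 1 TEAE for that treatment under the maximum severity recorded". It names no table or row to which it is confined, and no other rule says how events are to be counted.

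The same section keeps individual records visible: "All AEs will be listed". The protocol, in Section 8.4, has no collapsing rule. It says only that "The incidence of AEs will be presented by severity and by relationship to study drug as determined by the Investigator". SAP Section 10, which records changes from the protocol, mentions dose levels and nothing about counting events.

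**The concern.** A subject count and an event count answer different questions. Collapsing repeats is right for the first, because a subject with three headaches is still one subject with headache. Applied to the second, it turns the number-of-TEAEs row into the number of distinct pairs of subject and preferred term, which the label does not describe.

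Two things follow when a term recurs in a subject. The table total no longer agrees with the listing. In the severity table, only the worst grade of each subject-and-term pair survives, so the milder repeats disappear and the event mix shifts towards higher grades. At stake are the accuracy and labelling of a descriptive safety summary that readers will compare across ascending doses.

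**Working it through.** The documents give no figure on this point, so there is none to reproduce. The check applies the rule literally and sizes the result under stated assumptions.

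**Inputs from the documents**

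- Both subjects and events are summarised in the overview and severity tables (SAP 8.6.1).
- Repeats of a term within subject and treatment become one TEAE at maximum severity (SAP 8.6.1).
- "Subjects will participate in only 1 cohort" (SAP Section 4), and each subject receives a single dose. The restriction to the same treatment therefore covers the subject's whole postdose period.
- "Six subjects will participate in each cohort" (SAP Section 5).

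**Step 1: what the rule counts.** Reported number of TEAEs = number of distinct subject-by-preferred-term pairs. This can never exceed the number of events, and it is lower whenever a pair holds more than one event.

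**Step 2: a small example (invented data).** Subject 1 has headache at Grade 1, Grade 1 and Grade 2. Subject 2 has headache at Grade 1 and nausea at Grade 1.

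| | Every event counted | SAP rule |
|---|---|---|
| Subjects with a TEAE | 2 | 2 |
| Number of TEAEs | 5 | 3 |
| of which Grade 1 | 4 | 2 |
| of which Grade 2 | 1 | 1 |

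The subject count is unchanged. The Grade 2 share of events moves from 1/5 = 20% to 1/3 = 33%, only because two Grade 1 events were dropped.

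**Step 3: size of the shortfall.** Let m be the mean number of episodes per affected subject and term. With P pairs there are mP events, of which P are counted. Share dropped = (mP − P)/(mP) = (m − 1)/m. The documents give no value for m, so these are assumptions:

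- m = 1.0: 0/1.0 = 0%
- m = 1.2: 0.2/1.2 = 17%
- m = 1.5: 0.5/1.5 = 33%
- m = 2.0: 1.0/2.0 = 50%

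**Step 4: a second view, per cohort of six.** Assume that the number of events of one term per subject is Poisson with mean μ. The expected event count in the cohort is 6μ. The expected count under the rule is 6(1 − e^(−μ)), and the ratio of counted to true is (1 − e^(−μ))/μ.

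| μ (assumed) | True | Counted | Ratio |
|---|---|---|---|
| 0.1 | 0.6 | 0.57 | 0.952 |
| 0.25 | 1.5 | 1.33 | 0.885 |
| 0.5 | 3.0 | 2.36 | 0.787 |
| 1.0 | 6.0 | 3.79 | 0.632 |

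For an uncommon term the loss is about 5%. It becomes large only for a term that subjects report about once each on average.

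**Step 5: the pattern in the protocol's own data.** Protocol Section 1.5 describes the completed healthy-volunteer study: headache, nausea and vomiting, all in one subject. As described, that is three events and three distinct terms, so both methods give 3.

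**The case against.** The strongest reply is that the rule was written with subject counts in mind and would be programmed that way. The TFL shells, which are a separate document and were not available, may confine it to subject rows. That cannot be ruled out, but the text points the other way. The unit is one TEAE, not one subject. The tables by preferred term carry no severity, so the maximum-severity clause would do nothing there. The rule just before it, on missing severity, has the same opening and also deals with events.

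A second reply is that the collapsed figure is prespecified and reproducible, so only the label is at fault. This partly stands: relabelling the row as subject-by-term occurrences would also remove the contradiction. The plan, however, promises a number of TEAEs, and the rule does not deliver one.

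A third reply is that the rule may be there to stop a grade change in one continuing event from being counted twice. That purpose is sound and the fix should keep it. As worded, though, the rule also merges separate events. The documents do not say whether intermittent episodes or grade changes are entered as one record or several.

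A reader might go further and infer three things that the documents do not support.

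- *Recurrence is lost.* It is not. Every event is listed, with derived onset time and duration for TEAEs where dates allow, and with six subjects per cohort repeats can be read off the listing.
- *The primary endpoint is miscounted.* SAP Section 3.1 defines the endpoint as an assessment of safety and tolerability from several sources and names no event count.
- *Decisions are affected.* The escalation criteria in protocol Section 5.5 turn on numbers of subjects with qualifying toxicities and on concentrations, and SAP Section 8.6.6 plans no inferential safety analysis.

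**Conclusion.** The inconsistency is real and conditional. Read literally, SAP 8.6.1 asks for a number of TEAEs and then gives a rule that yields something else whenever a subject has a repeat of the same term. In that case the event counts, overall and by severity, are too low and do not agree with the listing. If no subject repeats a term, nothing is lost.

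The shortfall runs from 0% at m = 1.0 to 50% at m = 2.0. All of these values of m are assumed, and the one healthy-volunteer pattern described in the protocol corresponds to 0%. It would be wrong to say that the count will be too low, or that a third or a half of events will go missing. Subject frequencies, the subject tables by class and term, the listings and the escalation decisions do not depend on this event count. The conclusion assumes that the TFL shells do not already restrict the rule. Priority: minor.

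**What to change.** Split the rule in SAP 8.6.1 by the quantity it serves.

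- For numbers of subjects: a subject who has several TEAEs under one preferred term contributes once, at the worst grade.
- For the number of TEAEs: each distinct event contributes once, at its own worst grade. Records that only mark a change of grade within one continuing event are treated as a single event.

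The second clause matters. Counting every record without it could count one continuing event twice. The TFL shells should be checked for the same wording.

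The cost is one SAP sentence before the SAP is finalised, with no new data and no effect on any inferential result. The only downside is that reported event counts may be higher than under the present rule.
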